5.1. Hypotheses and Decision Rules

In this study, all hypothesis testing will use a two-sided test, unless specified otherwise.

The primary objective is to demonstrate the efficacy of a single infusion of PF-06838435 in male participants \geq 18 years of age with moderately severe to severe hemophilia B (FIX:C \leq 2%). The primary objective is addressed via the primary endpoint of ABR_{total}.

The hypothesis test of ABR_{total} is noninferiority test of pre- and post treatment with PF-06838435 with a noninferiority margin of 3.

A gatekeeping process will be applied to control multiplicity of testing multiple endpoints at the primary analysis. The subsequent hypothesis testing will only be performed after success on a previous hypothesis test, each test performed at the α defined for the primary analysis (0.05). The analyses cease when a failure occurs. The sequence of gatekeeping process is displayed in Table 2. For the last group of hypothesis tests, we would apply Hochberg (1988) step-up procedure so that the familywise error rate will be controlled under 0.05. Note, only selected endpoints are included in the sequence in the table below.

			Hypothes	is testing ce	eases when	a failure occ	ours		
ABR _{total} non- inferior to FIX prophyla xis regimen#	ABR _{treat} non- inferior to FIX prophylaxis regimen#	AIR superior ity to FIX prophyl axis regimen	Steady state FIX:C >5%*	FIX consump- tion superiority to FIX prophylaxi s regimen	ABR _{treat} superiority to FIX prophylaxi s regimen	ABR _{total} superiority to FIX prophylaxi s regimen	Haem-A- QoL Physical Health domain significantly improved from baseline	HAL Complex Lower extremity Activities compone nt score signifi- cantly improved from baseline	ABR _{total} of specific type (spontaneous , trauma, untreated, in target joints,) non-inferior to FIX prophylaxis regimen, and HJHS (Hochberg step-up method)

Table 2. Sequence of Gatekeeping Process of Multiple Hypothesis Tests

#The upper bound of the confidence interval of the difference in ABR_{total} and ABR_{treat} between pre- and post PF-06838435 will be compared to the NI margin. All other hypothesis tests are 2-sided tests. *Steady state FIX:C will be analyzed using a one-sided, one sample t-test.

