## 9.2. Sample Size Determination

Participants who complete the lead-in protocol C0371004 will be screened to achieve desired sample size of 40 participants, and eligible participants will be assigned to study intervention. All 40 participants are expected to be evaluable in this one-armed study.

When all 40 participants have completed at least 15 months of follow-up post-infusion of PF-06838435, the  $ABR_{total}$  data will provide at least 90% power (one-sided test with  $\alpha=0.025$ ) to demonstrate non-inferiority of gene therapy compared to prophylaxis treatment on the difference in  $ABR_{total}$ , using a repeated measure negative binomial regression, with a non-inferiority margin of 3.0 bleeds/year. The assumed background rate of annualized bleeding is a conservative 5.0 and the assumed annualized bleeding rate post-PF-06838435 is 1.5. The details of non-inferiority margin selection are included in [Appendix 10](#).

The number of participants may exceed 40, because all participants who complete the lead-in study (C0371004) and meet other eligibility criteria will be allowed to participate in this study.

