## 9.4. Statistical Analyses

The SAP will be developed and finalized before database lock and will describe the participant populations to be included in the analyses, any multiple testing procedures (to control the overall type I error of primary, secondary hypothesis test), and procedures for accounting for missing, unused, and spurious data. The overall probability of Type 1 error alpha for primary statistical tests, and other tests included in the multiple testing procedure, is controlled at .05 (or one-sided .025). Any minor changes to the statistical methodology stated in the protocol will be described in the SAP. This section is a summary of the planned statistical analyses of the primary and secondary endpoints.

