Secondary	
 
ABR for treated bleeds from Week 12 to Month 15 will be compared to pre-infusion of PF-06838435 (under SOC FIX prophylaxis replacement regimen) using a repeated measure negative binomial regression, with a non-inferiority margin of 3.0 bleeds/year.
 
AIR for FIX from Week 12 to Month 15 versus AIR during SOC FIX replacement regimen will be tested for superiority. Paired T-test will be used to do this hypothesis testing.
 
Vector-derived steady state FIX:C (Week 12 to Month 15) will be compared to a threshold of 5% using a one-sided, one sample T-test. FIX:C will be descriptively summarized by study visit.
 
FIX consumption, from Week 12 to Month 15, similar method as applied to AIR will be used to do hypothesis testing on this endpoint.
 
Number of bleeding events of specific type from Week 12 to Month 15: spontaneous and traumatic, and untreated. Similar method applied to ABRtotal will be used to test these endpoints.
 
Frequency of target joint bleeds from Week 12 to Month 15 will be summarized. The number of target joints bleeds will be compared to baseline. Similar method applied to ABRtotal will be used to test these endpoints.
 
Percentage of participants without bleeds (total bleeds and treated bleeds) will be summarized by type from Week 12 to Month 15.
 
HJHS for first 12 months post-infusion of PF-06838435 will be compared to baseline using 2-sided paired T-test.
 
PRO endpoints (Haem-A-QoL Physical Health domain, HAL Complex Lower Extremity Activities Component Score) 12 months post-infusion of PF-06838435
 

Endpoint	Primary analysis Statistical Analysis Methods
	will be summarized and compared to baseline to assess the improvement from baseline if baseline is available.
Exploratory	
 
Will be described in the statistical analysis plan.
 

Final analysis	

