6.2.3. FIX:C

6.2.3.1. Main Analysis

A log transformation of the steady state FIX:C (as the endpoint defined in Section 3, the geometric mean is the antilog of the mean of the log-transformed values) will be compared to a threshold of log(5) using a one-sided, one-sample t-test.

- The Dosed population will be the primary analysis population. Analysis will also be done on the Evaluable population if it is different from Dosed population.
- The sample size, mean and t-based 95% CI, standard deviation, median, Q1, Q3, minimum, and maximum of FIX:C (all descriptive statistics will be transformed back to original scale) will be presented in the summary tables. For the primary analysis,

assessments with missing data imputation will be utilized. Another supportive analysis will also be conducted with only observed data.

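### The SAP gives no one-sided level for the steady-state FIX:C test: its stated rules lead to one-sided 0.05, where the protocol sets one-sided 0.025

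*SAP*

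**What the plan says.** **SAP section 5.1.** Tests are two-sided unless specified otherwise, and the hierarchy is run in a fixed order, "each test performed at the α defined for the primary analysis (0.05"). The 0.05 carries no statement of sidedness. The Table 2 footnote explains that the ABR non-inferiority steps compare an upper confidence bound with the margin. It continues "All other hypothesis tests are 2-sided tests", and then sets FIX:C apart: "Steady state FIX:C will be analyzed using a one-sided, one sample t-test".

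**SAP section 6.2.3.1.** The log-transformed endpoint is compared with a "threshold of log(5) using a one-sided, one-sample t-test". No level is given here either. The summary table is to contain "The sample size, mean and t-based 95% CI, standard deviation" and other descriptive statistics. The interval is listed as output, not as the decision rule.

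**Protocol.** Section 9.4 says that the type I error for the primary tests, and for "other tests included in the multiple testing procedure, is controlled at .05 (or one-sided .025"). Section 9.2 powers the primary comparison at one-sided 0.025 ("will provide at least 90% power (one-sided test with" α = 0.025). Section 9.4.1 says that FIX:C "will be compared to a threshold of 5% using a one-sided, one sample T-test", with no level.

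**The concern.** A programmer who follows the SAP finds one level (0.05) for every step and one direction (one-sided) for FIX:C, and compares a one-sided p-value with 0.05. That is twice the protocol's one-sided level. Among the individually tested steps, FIX:C would then be the only one allowed 0.05 in the favourable direction: the non-inferiority steps use a bound of a 95% CI, and a two-sided test at 0.05 leaves 0.025 in the favourable tail.

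FIX:C is step 4 of 10. Six steps follow it: FIX consumption, superiority on treated bleeds, superiority on total bleeds, Haem-A-QoL Physical Health, HAL Complex Lower Extremity, and the final Hochberg group. The study is open label, so a pass threshold settled only after data have accrued is open to challenge.

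**Working it through.** **The protocol's level.** 0.05 / 2 = 0.025. The normal quantile is 1.960 for two-sided 0.05 and also for one-sided 0.025. It is 1.645 for one-sided 0.05, so the protocol's pair of figures is consistent and one-sided 0.05 is a different level.

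**Inputs**
- n = 40 (protocol 9.2). The protocol allows more, so n = 45 is run as an illustration.
- Threshold 5%, tested on the log scale (SAP 6.2.3.1).
- Phase 1/2 steady-state FIX:C of 33.7 ± 18.5% (protocol 2.2.2).
- Imputed value 1.9% after withdrawal, dropout or resumed prophylaxis (SAP 3.2.3).
- Assumption: FIX:C is log-normal. Neither document gives a log-SD, so 1.0 is also shown.

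**Log-scale values from Phase 1/2**
- CV = 18.5 / 33.7 = 0.549
- log-SD = √ln(1 + 0.549²) = 0.513
- geometric mean = 33.7 / √(1 + 0.549²) = 29.5%

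**Lowest passing geometric mean** = 5 × exp(t × SD / √n)

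| n | df | log-SD | One-sided 0.05 | One-sided 0.025 |
|---|---|---|---|---|
| 40 | 39 | 0.513 | t = 1.685, 5.73% | t = 2.023, 5.89% |
| 40 | 39 | 1.0 | 6.53% | 6.88% |
| 45 | 44 | 0.513 | t = 1.680, 5.69% | t = 2.015, 5.83% |
| 45 | 44 | 1.0 | 6.42% | 6.75% |

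**Error and power (n = 40, log-SD 0.513).** In 400,000 simulated trials with a true geometric mean of 5%, the false-claim rate was 0.0497 at one-sided 0.05 and 0.0247 at one-sided 0.025. Power at a true 6% is 0.71 against 0.59. At the Phase 1/2 geometric mean it is about 1.00 at both levels.

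**How many failures before the level matters.** Set f of 40 participants at 1.9% for the whole Week 12 to Month 15 window. Give the others mean ln 29.5 and SD 0.513. Test against ln 5, with 95% CI = exp(mean ± 2.023 × SE).

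| f | t | One-sided p | Geometric mean (95% CI) | Pass at 0.05 | Pass at 0.025 |
|---|---|---|---|---|---|
| 0 | 21.9 | <0.001 | 29.5% | yes | yes |
| 8 | 6.46 | <0.001 | 17.1% | yes | yes |
| 19 | 2.08 | 0.022 | 8.0% (5.07 to 12.7) | yes | yes |
| 20 | 1.78 | 0.041 | 7.5% (4.73 to 11.9) | yes | no |
| 21 | 1.48 | 0.073 | 7.0% (4.43 to 11.1) | no | no |

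In this model the decision differs at one count only, 20 of 40. There the test passes at one-sided 0.05 while the reported 95% CI includes 5%.

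**The case against.** The strongest reply is that 0.05 in the SAP is the name of a two-sided level. The text ties it to the primary analysis. That analysis is decided on the upper bound of a 95% CI (SAP 6.1.1.1), and the example code in SAP Appendix 1.1 sets alpha = 0.05 for that interval. The directional primary decision is therefore already one-sided 0.025, and the same convention applied to FIX:C gives 0.025. Protocol 9.4 states the equivalence outright, and the SAP's version history lists no change of alpha for FIX:C. On that reading the test and the reported CI agree.

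This is plausible and is probably what was meant. It remains an inference. The footnote tells the reader that FIX:C is not one of the two-sided tests, and for this endpoint, unlike the ABR steps, no rule based on a confidence bound is given. The SAP also says that it may modify the protocol's plans, so a reader cannot be sure whether the difference is intended.

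Two further replies stand. First, one-sided 0.05 in a fixed sequence does not take nominal familywise error above 0.05. Second, the failure model above is severe. SAP 3.2.3 imputes 1.9% only at visits after the event. If failures are imputed for half the window, each such participant's geometric mean is √(1.9 × 29.5) ≈ 7.5%, and every count up to 39 of 40 passes at both levels.

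**Conclusion.** The point holds. The SAP omits the one-sided level for a confirmatory step, and its stated rules lead to one-sided 0.05 where the protocol sets one-sided 0.025. The consequences are a doubled chance of a false claim that FIX:C exceeds 5% (0.05 instead of 0.025) and a possible pass beside a 95% CI that includes 5%.

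The practical effect is small. The pass threshold moves by 0.16 percentage points at log-SD 0.513 (5.89 − 5.73) and by 0.35 at log-SD 1.0 (6.88 − 6.53). The decision is very unlikely to change if FIX:C is anywhere near the Phase 1/2 level. These sizes rest on log-normal values, 40 participants and a log-SD taken from 10 Phase 1/2 participants. The textual conflict does not depend on them.

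**What to change.** - **SAP 5.1:** state that 0.05 is the two-sided level and that the one-sided FIX:C test uses α = 0.025.
- **SAP Table 2 footnote and section 6.2.3.1:** repeat this with the equivalent rule, that FIX:C succeeds if the lower limit of the two-sided 95% CI of the geometric mean exceeds 5%.

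The endpoint, the test and the order of the hierarchy do not change. The cost is wording in three places before database lock, with no new data or analysis, because the 95% CI is already planned. The one downside is that a result in the narrow band between the two thresholds, for example a geometric mean from 5.73% to just under 5.89% at log-SD 0.513 with 40 participants, would no longer pass.

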### 3. OBJECTIVES, ESTIMANDS, AND ENDPOINTS

Objectives	Endpoints

Primary
 
 
To demonstrate the efficacy of a single infusion of PF-06838435 in male participants <math>\geq 18</math> years of age with moderately severe to severe hemophilia B (FIX:C <math>\leq 2\%</math>).
 
	
Primary
 
Primary endpoint:
 
 
Non-inferiority on annualized bleeding rate (ABR) for total bleeds (treated and untreated) from Week 12 to Month 15 versus standard of care (SOC) FIX prophylaxis replacement regimen, comparing pre- and post-IP infusion.
 

Secondary
 
 
Key secondary objectives: To demonstrate the efficacy of PF-06838435 in terms of the use of exogenous FIX, the treated bleeds, and FIX:C.
 
	
Secondary
 
 
Key secondary endpoints:                             
 
Non-inferiority on ABR for treated bleeds from Week 12 to Month 15 versus SOC FIX prophylaxis replacement regimen, comparing pre- and post-IP infusion.
 
Annualized infusion rate (AIR) of exogenous FIX from Week 12 to Month 15 versus AIR of FIX with SOC FIX replacement regimen pre-IP infusion.
 
Vector-derived FIX:C level at steady state (from Week 12 to 15 months) demonstrated to be greater than 5%. FIX:C will also be summarized descriptively by study visit.
 
 
 

 
To compare additional efficacy parameters post-PF-06838435 infusion to baseline in order to further characterize PF-06838435 treatment, including use of exogenous FIX, information on bleeding events, and patient reported outcomes addressing health related quality of life, activities of daily living and general health status.
 
	
The following parameters will be compared with SOC FIX replacement regimen, comparing pre- and post-IP infusion from Week 12 to Month 15:
 
 
Annualized FIX consumption.
 
Annualized number of bleeding events of specific type: spontaneous and traumatic, and untreated.
 
Frequency of target joint bleeds.
 
Percentage of the participants without bleeds.
 
 
The following parameters will be compared with SOC FIX replacement regimen, comparing pre- and post-IP infusion at 12 months:

Objectives	Endpoints

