## 10.10. Appendix 10: Non-Inferiority Margin Selection

The choice of the non-inferiority margin is based on the consideration of the following guidelines. The constancy assumption was taken into consideration and the “95%-95%” method is used.

- FDA guideline for selecting a margin based on historical data.
- EMA guidelines on the choice of non-inferiority margin.
- International Conference on Harmonization (ICH) Note for Guidance E9 (Statistical Principles for Clinical Trials).
- ICH Note for Guidance E10 (Choice of Control Group).
- CPMP Points to Consider on Switching Between Superiority and Non-Inferiority.

The non-inferiority margin will be based on the effect of prophylaxis treatment over on-demand treatment (as the reference treatment). This will be expressed via a mean difference in ABR in a single arm trial with a switch from on-demand to prophylaxis using a paired comparison. This design reflects the Committee for Medicinal Products for Human (CHMP) guidance for the design of prophylaxis clinical trials. Based on the lower bound of the confidence interval of an estimate for the ABR for treated bleeds (referred to as  $ABR_{treat}$ ) in on-demand participants, the  $ABR_{treat}$  is assumed to be higher by at least CCI, which will be considered as  $M_1$  in the non-inferiority test setting for the  $ABR_{treat}$ . It is assumed that the treatment difference (on-demand – prophylaxis) in  $ABR_{total}$  is proportional to that in  $ABR_{treat}$ . The ratio of the treatment difference ( $ABR_{total}$  over  $ABR_{treat}$ ) is estimated to be CCI. Thus  $M_1$  for  $ABR_{total}$  is estimated to be CCI.

Given the large effect size of prophylaxis treatment (over on-demand therapy), an appropriate value for  $M_2$  will be considered in order to preserve a sufficiently large proportion of this effect. Simulations have been conducted to assess preservation levels of CCI of  $M_1$ . These percentages correspond to non-inferiority margin values of CCI bleeding events/year respectively, on an absolute scale. A value of 3.0 for  $M_2$  (approximately CCI of the  $M_1$  effect preserved) is proposed as both clinically meaningful and yielding a reasonable sample size for establishing efficacy.

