3.2.5. Annualized Bleeding Rate of Specific Type of Bleeding

Other secondary endpoints, such as annualized bleeding events (ABR_{total}) of a specific type: by cause: spontaneous, traumatic; by location: in joint (including target joints), in soft tissue, and untreated bleeding, as defined in the Protocol Appendix 7, will be calculated and summarized. The data collection and endpoint derivation are similar to those described for ABR_{total}. The baseline for each specific type of bleeding episode will be derived similarly as defined for ABR_{total}, with baseline of these endpoints obtained from the Pre-Infusion Period. The investigators will assess the health of the joint(s), identified target joints (Section 3.3.1.1) at baseline prior to PF-06838435 infusion. Any bleeding occurring during the study into the identified baseline target joints will be considered as target joint bleeds and will be summarized.

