6. ANALYSES AND SUMMARIES

6.1. Primary Endpoint(s)

6.1.1. ABR for Total Bleeds

6.1.1.1. Main Analysis

ABR_{total} will be analyzed using a repeated measures generalized linear model with negative binomial distribution and identity link function. Treatment (prophylaxis, or PF-06838435) and duration will be included in the model. Treatment will be a class factor in the model, duration is numeric and participant will be a random effect. Duration is the elapsed time in years of each treatment period. Duration is at least 0.5 for pre-PF-06838435 infusion prophylaxis which corresponds to six months. This period begins at enrollment of the lead-in study and ends on date of PF-06838435 infusion. Duration of PF-06838435 period is the observed time from Week 12 (Day 82) until cutoff for the specified analysis (e.g. 15 months for the primary analysis) or the date of study withdrawal or resumption of FIX infusion (whichever is earlier), minus any time that is predefined to be excluded.

- The Dosed population will be the primary analysis population. Analysis will be repeated for the Evaluable population if it is different from Dosed population.
- The mean ABR_{total} from Week 12 to Month 15 will be compared to the pre-infusion mean via the estimation of the mean difference and 95% CI. If the upper bound of the confidence interval of the difference of (ABR_{total} PF-06838435 ABR_{total} FIX prophylaxis) is smaller than 3.0, then statistical significance of the noninferiority claim would be demonstrated. An example of SAS code of such analysis is included in the Appendix 1.1. If noninferiority is demonstrated, further testing for superiority would be conducted after the primary analysis (assuming other endpoints within the

testing hierarchy are statistically significant), using the same method, except the margin would be modified to 0.

• The summary table will include two columns, for FIX prophylaxis and PF-06838435, respectively. The summary statistics in the table will include n, mean, median, Q1, Q3, range of the observed ABR_{total}, model derived mean ABR_{total} and 95% CI, estimated mean difference (model derived), and the 95% CI of the mean difference (model derived).

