6.2.5. Annualized Bleeding Rate of Specific Type

The ABR_{total} of specific types such as spontaneous bleeding, traumatic bleeding, bleeding in joints, bleeding in soft tissue, and untreated bleeding etc. These endpoints will be analyzed similarly as defined for main analysis of ABR_{total}.

These analyses will be conducted on Dosed population.

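### The last step of SAP Table 2 calls four bleed subtypes non-inferior without a subtype margin, and the 3.0/yr reached by cross-reference is justified only for treated and total bleeds

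*SAP*

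**What the plan says.** SAP 5.1 sets out a fixed sequence of tests in Table 2. The final step is a group tested by Hochberg's procedure at a familywise 0.05. It holds the rates of spontaneous, traumatic, untreated and target-joint bleeds, plus HJHS, and its label reads "trauma, untreated, in target joints,) non-inferior to FIX prophylaxis regimen, and HJHS (Hochberg step-up method". No number accompanies the word non-inferior.

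The # mark in Table 2 sits on the first two columns only. Its footnote says the upper confidence bound for ABRtotal and ABRtreat "will be compared to the NI margin. All other hypothesis tests are 2-sided tests".

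For the subtypes, SAP 6.2.5 says: "These endpoints will be analyzed similarly as defined for main analysis of" ABRtotal. That main analysis (SAP 6.1.1.1) has one non-inferiority rule: if the upper bound of the difference "is smaller than 3.0, then statistical significance of the noninferiority claim would be demonstrated". SAP 3.2.5 derives the subtypes as for ABRtotal, listing them "by cause: spontaneous, traumatic; by location: in joint (including target joints), in soft tissue, and untreated bleeding". Protocol 9.4.1 treats target joints the same way: "The number of target joints bleeds will be compared to baseline. Similar method applied to" ABRtotal.

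Protocol Section 3 frames only ABRtotal and ABRtreat as non-inferiority endpoints. It introduces the subtypes with "The following parameters will be compared with SOC FIX replacement regimen, comparing pre- and post-IP infusion from Week 12 to Month 15".

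On the origin of 3.0, Protocol Appendix 10 says: "The non-inferiority margin will be based on the effect of prophylaxis treatment over on-demand treatment (as the reference treatment"). It takes that effect for treated bleeds, scales it to total bleeds by an assumed ratio, and supports the result with treated-bleed and total-bleed rates.

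**The concern.** A non-inferiority claim means only as much as its margin. Here the label, the footnote and the cross-reference point in different directions. Under the label and SAP 6.2.5 the subtypes are tested against 3.0; under the footnote they are tested two-sided, which for a comparison of two rates means against zero. These are different hypotheses, and a programmer cannot tell which p-value should enter Hochberg beside the HJHS paired t-test.

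If 3.0 is applied, it is borrowed. It was argued from the effect of prophylaxis over on-demand treatment on all treated or all bleeds. Each subtype is only part of the total, and the visible text gives no corresponding effect for any of them. Because the step sits inside the familywise-controlled sequence, a pass could be reported as a confirmatory statement that, say, untreated or target-joint bleeding is no worse than on prophylaxis, although the test could hardly have failed.

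**Working it through.** **Inputs from the documents.** Rates 5.0/yr before and 1.5/yr after, n = 40, margin 3.0, one-sided 0.025 (Protocol 9.2). Pre-infusion exposure at least 0.5 yr (SAP 6.1.1.1). Post-infusion exposure Day 82 to Day 469 = 388 days = 388/365.25 = 1.062 yr (SAP 5.2). Hochberg group: 4 subtypes + HJHS = 5 tests, so the strictest level is 0.05/5 = 0.01.

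**Assumed, because the documents give no values.** Negative binomial dispersion k and all subtype rates.

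**1. The plan's own power figure.** Protocol 9.2 states at least 90% power for ABRtotal. Approximate check, with pre and post counts independent:
- SE² = [(m1 + k·m1²)/t1² + (m2 + k·m2²)/t2²]/40, where m = rate × time
- power = Φ((3.0 − (1.5 − 5.0))/SE − 1.96) = Φ(6.5/SE − 1.96)
- At k = 3: m1 = 2.5, m2 = 1.593; SE² = (85.0 + 8.16)/40 = 2.33; SE = 1.526; power = Φ(2.30) = 98.9%
- At k = 2 it is 99.9%; at k = 5, 92.3%; it reaches 90% near k = 5.5.

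The stated figure is therefore plausible, and it concerns ABRtotal only. No figure is stated for any subtype.

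**2. What 3.0 means for a subtype (no dispersion needed).**
- Protocol Appendix 7 defines two causes, spontaneous and traumatic. At 5.0/yr the smaller is at most 5.0/2 = 2.5/yr. So 3.0 is at least 3.0/2.5 = 120% of its starting rate, against 3.0/5.0 = 60% for total bleeds.
- At 1.5/yr for all bleeds after infusion, no subtype can exceed 1.5/yr. Its largest possible true increase is 1.5 − 0 = 1.5/yr, and 1.5/3.0 = 50% of the margin. (This ignores the SAP 3.1.1 rule by which simultaneous treated bleeds at several sites count once overall but at each site in site summaries.)

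At the planned rates, subtype non-inferiority at 3.0 is thus true by construction.

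**3. How often a worsening would pass.** Take a true tripling from 0.5 to 1.5/yr (difference 1.0).
- Closed form: k = 1, SE = 0.350, Φ(2.0/0.350 − 1.96) > 99.9%; k = 3, SE = 0.498, Φ(2.0/0.498 − 1.96) = 98.0%.
- Gamma-Poisson simulation: 20,000 replicates in each of 12 settings (k = 1, 2, 3; pre-infusion exposure 0.5 or 0.75 yr; shared or independent participant effects), using a rate difference with participant-level standard error. Non-inferiority is declared in 93-100% of trials at two-sided 0.05 and in about 85-100% at 0.01. The 95% CI lies wholly above zero, with non-inferiority still declared, in about 52-98%.
- Extreme case allowed by the planned rates, a subtype absent before infusion that makes up every bleed after it (0 to 1.5/yr): declared non-inferior in 83-98%, or 72-95% at 0.01.

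**4. Cost of testing against zero.** For a 70% reduction from 0.5 to 0.15/yr, simulated superiority power is about 34-70% at two-sided 0.05 and 9-40% at 0.01.

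**The case against.** **The margin is given by reference.** SAP 6.2.5 does lead to 3.0, and the column heading refers to ABRtotal of specific type, so a lenient reader could bring it under the footnote. That answers which number is meant, but not why it suits a subtype. If the footnote is read literally instead, the label is wrong. The text needs correcting either way.

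**Sidedness is immaterial.** This stands. Comparing the upper limit of a two-sided 95% CI with a margin is a one-sided 0.025 test, and Protocol 9.4 treats the two as one level. The two-sided wording alone changes no error rate. What differs is the null value, 3.0 or 0, and hence the p-value that enters Hochberg.

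**The pass rates are not errors.** This also stands. A reader might infer that 93-100% is a false-positive rate or that the familywise error is inflated. It is neither: a true difference of 1.0 or 1.5 lies inside 3.0, so the declaration is correct at that margin. The complaint is that the margin is too loose for the claim to inform. The CI would be tabulated, so a careful reader could see a worsening that the label hides.

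**Earlier steps protect.** In part. Superiority on ABRtreat and ABRtotal must come first, and a subtype rise large enough to hold total bleeds near 5.0/yr would rarely get through. Those tests do not constrain a small subtype. In an illustrative run (untreated 0.25 to 0.75/yr, treated 4.75 to 0.75/yr), trials passing both superiority tests declared non-inferiority for untreated bleeds about 100% of the time, with the CI wholly above zero in 39-85%. The split is assumed, and the AIR, FIX:C, FIX consumption and PRO steps were not simulated.

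**The simulation is not the planned model.** Correct: SAP 6.1.1.1 specifies an identity-link negative binomial model. The two results in step 2 of the working do not depend on any model.

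**Conclusion.** The point holds. Table 2's last step makes a confirmatory non-inferiority claim for four bleed subtypes without a stated margin. The only margin reachable by cross-reference has no visible justification for them, and the table's footnote does not include them in the margin comparison. At the planned rates a pass at 3.0 is nearly automatic: the largest possible true increase is half the margin. That rests on document figures alone; the 93-100% pass rate rests on the assumed dispersion, exposure and subtype rates.

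Two stronger readings are not supported. A reader might infer that 3.0 exceeds the whole effect of prophylaxis on a subtype. The documents give no such effect, and the numbers behind the total and treated effects are redacted, so this cannot be judged. A reader might also infer that the main conclusions are weakened. They are not: the primary and key secondary tests have their own stated margin, null value or threshold and come earlier in the sequence. The scope is last-step secondary claims only, and the matter is worth correcting without being critical.

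**What to change.** Before database lock, revise the SAP as follows:
- In Table 2, relabel the last step so that the four subtypes are tested for superiority (margin 0, two-sided), which matches the footnote. State that these two-sided p-values enter the Hochberg step beside HJHS.
- In SAP 6.2.5, state that the 3.0 margin does not apply to the subtypes.
- If the sponsor does not want superiority tests, take the subtypes out of the confirmatory sequence and report estimates with 95% CIs.

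Data collection does not change. The cost is that fewer last-step claims may reach significance. The power in step 4 of the working is for a low-rate subtype; for a 70% reduction from 2.5/yr it is about 67-100% at two-sided 0.05. Reporting estimates only gives up confirmatory subtype claims altogether.
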